4.4.4 Other analyses for primary endpoint

4.4.4.1 Analysis of change from baseline in HbA1c at Week 6, Week 12, and Week 20

Additional analyses for change from baseline in HbA1c will be performed at Week 6, Week 12 and Week 20. Data will be multiply imputed based on the same approach as described for the primary analysis in Section 4.4.1, and will include all data regardless of rescue medication initiation or adherence. Analysis will be based on the same multiply imputed data sets produced for the primary analysis of the primary endpoint. Analysis will be performed by fitting the ANCOVA model described for the primary endpoint in Section 4.1.9. The analysis model will be evaluated in each imputed data set and the results will be combined using Rubin's rules as described in Section 4.1.12.4 for each visit.

In addition, a line plot of LS mean \pm 95% confidence interval (CI) by visit up to Week 26 will be displayed.

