4.1.12 Multiple imputation

Missing quantitative Week t data at study endpoint will be imputed from one of the 2 missing not at random (MNAR) imputation models for missing Week t data.

The preferred model will be to use a "retrieved drop-out" multiple imputation (MI-RD) model to represent the MNAR process. This will be used if there is sufficient data from 'retrieved drop-outs', defined as subjects who discontinued the treatment (but not the study) and had a Week t HbA1c value. If any of the required imputation models needed for any of the regimens (low, low/high, overall) within dapagliflozin or saxagliptin have less than 5 retrieved drop-out

observations available to fit the model, then MI-WO “wash-out” method will be used for analyses of all regimens for that endpoint. This is a “copy to reference method”. Both MI-RD or MI-WO will be implemented using a baseline to predict Week t values in the MNAR model. The randomisation strata will be coded using indicator variables as follows and used in the multiple imputation steps:

- randomisation strata of background medication will be coded as
 - met (1) and ins (0) if metformin only,
 - met (0) and ins (1) if insulin only,
 - met (0) and ins (0) if metformin + insulin;
- randomisation strata of background medication if randomisation strata of insulin only and insulin with metformin are grouped will be coded as
 - metins (1) if metformin only,
 - metins (0) if insulin only or insulin with metformin;
- randomisation strata of age group will be coded as
 - age (1) if age ≥ 10 and < 15 years,
 - age (0) if age ≥ 15 and < 18 years;
- randomisation strata of sex will be coded as
 - sex (1) if male,
 - sex (0) if female.

Each imputation model will use a common seed value of 2717.

In case of non-convergence because of sparse data, subsequent backup imputation models will be used in removing randomisation strata in sequential order and/or collapsing the randomisation strata of background medication as defined in Section 4.1. A subsequent back-up model in the order presented Section 4.1 will only be provided if the preceding back-up model does not converge.

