4.1.12.1 Monotone Data Pattern

Prior to imputation, intermittent missing HbA1c/FPG values (i.e., missing values both preceded and followed by at least one non-missing value) will be imputed under a “missing at random” (MAR) model for missing data using a Markov chain Monte Carlo (MCMC) method of imputation.

Since in general the missing pattern will not be monotone, the first step for any of the methods presented below will be to use the Markov Chain Monte Carlo (MCMC) method in conjunction

with the MONOTONE statement of the SAS MI procedure to partially impute quantitative parameters, separately for each treatment regimen (i.e. low-dose, low-dose/high-dose and placebo) and by weight, to create imputed datasets with just enough missing quantitative values to generate two hundred (200) imputed data sets with a monotone missing data pattern (for each treatment regimen), assuming a MAR missing data pattern. Subjects withdrawing from IP before the up-titration will be assigned a weight of 1 and will be included in each imputation model (low-dose and low-dose/high-dose regimen). Indicators of randomisation strata (as described in Section 4.1.12) and visit (i.e., baseline HbA1c/FPG along with all visits per protocol up to Week t) will be the parameters included in MCMC models.

The random seed number for the MCMC stage will be 2717.

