4.1.12.3 Wash-out multiple imputation method

Using the monotone datasets generated as described in Section 4.1.12.1, the remaining missing data will be imputed separately for each treatment group using a REGRESSION method in conjunction with the MONOTONE statement and either MNAR statement (for dapagliflozin/saxagliptin treatment groups) or MAR (for placebo treatment group) of the SAS MI procedure. Weight will not be included in the imputation model.

- Step 1: The imputation model used to create monotone data pattern (see Section 4.1.12.1) will include factors and covariate in the following order: indicators representing randomisation strata of sex, age group and background medication, baseline HbA1c/FPG as well as HbA1c/FPG from all visits per protocol up to Week t.
- Step 2: For subjects from dapagliflozin/saxagliptin treatment group, Week t data from the placebo group subjects with non-missing baseline will be used in modelling the MNAR process. The imputation model will include, in the following order, indicators representing randomisation strata of sex, age group and background medication as well as, baseline HbA1c/FPG and Week t HbA1c/FPG.

While for subjects from placebo treatment group, missing data will be imputed sequentially at each assessment using a MAR imputation based on all non-missing data from that visit and data from all prior visits (after imputation). The indicators representing randomisation strata will be included in modelling the MAR processes in the same order as described in Step 1. Therefore, the model will include, in the following order, indicators representing randomisation strata of sex, age group and background medication as well as, baseline HbA1c/FPG, and HbA1c/FPG from all visits per protocol prior to and including Week t.

- Step 3: Imputed values from each of the 200 imputation datasets selected from Step 2 and the non-missing data will be analysed by ANCOVA applied at Week t, with terms for baseline HbA1c/FPG, randomisation strata and treatment group as described in Section 4.1.9. In case of non-convergence, the imputation and ANCOVA model will be simplified by removing/collapsing the randomisation strata indicator variables in a stepwise manner as described in Section 4.1.
- Step 4: Results from each ANCOVA model will be combined as described in Section 4.1.12.4.

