4.4 Primary efficacy endpoint analysis

4.4.1 Primary analysis of the primary endpoint

The primary efficacy analysis will compare the mean reduction in HbA1c from baseline at Week 26 between overall drug treatment (low-dose and high-dose) and placebo. The ITT estimand (which will be estimated using data regardless of premature treatment discontinuation, regardless of rescue medication initiation and with multiple imputation) will be evaluated as the primary estimand.

Listings of HbA1c and FPG results used for the efficacy analysis will be presented with flags to identify data collected prior to rescue medication initiation or treatment discontinuation.

The primary efficacy analysis will be performed using an ANCOVA model, as described in Section 4.1.9. Separate models will be used for dapagliflozin and saxagliptin analyses, and each analysis will include the (common) placebo control. Each model will have terms for baseline HbA1c value, treatment group, and randomisation strata variables (age group, sex and background medication). Missing values for Week 26 will be imputed using multiple imputation method assuming the data are not missing at random. No weights will be used in the multiple imputation or ANCOVA for this analysis.

An overview of the analysis steps are as follows:

- i) Impute missing Week 26 HbA1c data using multiple imputation (as described in Section 4.1.12).
- ii) Analyse data by applying the ANCOVA model (described in Section 4.1.9) in each of the imputed data sets to calculate the LS means and corresponding SEs for the adjusted mean changes within each treatment group as well as for the differences in adjusted mean changes

between treatment groups. If any stratification variables in the imputation model are collapsed, then the ANCOVA model will be collapsed correspondingly.

- iii) Combine point estimates and SEs using Rubin's rules (as per Section 4.1.12.4) to produce valid global estimates with corresponding p-values and CIs.

Combined LS means and 95% confidence intervals for the mean change in HbA1c for each treatment group as well as the difference in the estimated mean change between the dapagliflozin/saxagliptin treatment group and placebo will be calculated. The p-value of the difference in Week 26 estimates between dapagliflozin/saxagliptin and placebo will be presented.

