4.6.2.1 Analysis of change from baseline at Week 52 in HbA1c and FPG

Change from baseline at Week 52 in HbA1c and, separately, FPG will be analysed using the ANCOVA model described in Section 4.1.9. This analysis includes all data regardless of rescue medication initiation or adherence. The analysis will be evaluated in each imputed data set and the results will be combined using Rubin's rules as described in Section 4.1.12.4. Missing data in values of HbA1c at Week 52 will be imputed using the multiple imputation approach described in Section 4.1.12. Point estimates and 2-sided 95% CIs for the mean change within each treatment group, as well as the difference in mean change between each drug and placebo will be calculated. Nominal p-values will be presented. No weights will be used in the multiple imputation or ANCOVA for this analysis.

Additional analyses for change from baseline in HbA1c and FPG will be performed at Week 6, Week 12, Week 20, Week 26, Week 32 and Week 40. Data will be multiply imputed based on the same approach as described for the in Section 4.5.4, and will include all data regardless of rescue medication initiation or adherence. Analyses will be based on the same multiply imputed data sets produced for Week 52 assessments. Analysis will be performed by fitting the same ANCOVA model as the one described above and in Section 4.1.9. The analysis model will be evaluated in each imputed data set and the results will be combined using Rubin's rules as described in Section 4.1.12.4 for each visit.

In addition, a line plot of LS means \pm 95% confidence interval (CI) by visit up to Week 52 will be displayed for both HbA1c and FPG.

4.6.2.2 Analysis of the percentage of subjects with baseline HbA1c \geq 7% who achieve a HbA1c level $<$ 7% at Week 52

Data will be multiply imputed based using the same approach as described for the primary analysis in Section 4.4.1, and will include all data regardless of rescue medication initiation or adherence. HbA1c response ($<$ 7%) will be derived from dichotomising the imputed continuous values of HbA1c and Rubin's rules will be used to combine analyses across the multiple imputations. The proportion of responders (subjects achieving an HbA1c $<$ 7% at Week 52) will be analysed using logistic regression and summarised as described in Section 4.1.10. No weights will be used in the multiple imputation or logistic regression for this analysis.

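### Under the wash-out method, the Week 6, 12 and 20 HbA1c analyses reuse data sets in which active-arm drop-outs are imputed only at Week 26 but placebo drop-outs at every visit

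*SAP*

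**What the plan says.** SAP 4.4.4.1 plans ANCOVAs of change in HbA1c at Weeks 6, 12 and 20 and a line plot of LS means up to Week 26. Two sentences govern the missing data: "Data will be multiply imputed based on the same approach as described for the primary analysis in Section 4.4.1", and then "Analysis will be based on the same multiply imputed data sets produced for the primary analysis of the primary endpoint".

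The primary analysis in SAP 4.4.1 has a single target visit: "Impute missing Week 26 HbA1c data using multiple imputation (as described in Section 4.1.12"). SAP 4.1.12 has the same scope: "Missing quantitative Week t data at study endpoint will be imputed from one of the 2 missing not at random (MNAR) imputation models".

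The wash-out method then works in two stages.

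- **MCMC pre-step (SAP 4.1.12.1).** Before the main imputation, "intermittent missing HbA1c/FPG values (i.e., missing values both preceded and followed by at least one non-missing value) will be imputed" under MAR. Values after a subject's last observed visit stay missing.
- **Step 2 (SAP 4.1.12.3).** For active subjects the model holds the strata indicators for sex, age group and "background medication as well as, baseline HbA1c/FPG and Week t HbA1c/FPG". No visit between baseline and Week t appears. For placebo subjects, "missing data will be imputed sequentially at each assessment using a MAR imputation".

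Table 23 lists the by-visit figure as supportive and as based on the Randomised Subjects Dataset.

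**The concern.** With t = 26, an active subject who leaves after Week 6 has a value at Week 26, drawn from the placebo model, but none at Weeks 12 and 20. A placebo subject who leaves at the same time has a value at every visit. Data sets built this way serve the Week 26 test, but at Weeks 12 and 20 the two arms have been handled by different rules.

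The stake is how the plotted time course is read. The active curve follows subjects with data up to Week 20. At Week 26 it takes in everyone, with the drop-outs carrying placebo-like values. A reader could take the resulting step for a waning effect. The figure is also described as covering all randomised subjects, which would not be true of the active arm before Week 26.

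**Working it through.** **Which visits each step fills, with t = 26**

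| Missing value | Active, wash-out | Placebo, wash-out | Either arm, MI-RD |
|---|---|---|---|
| Intermittent gap | filled (MCMC) | filled (MCMC) | filled (MCMC) |
| Week 6, 12 or 20 after drop-out | not filled | filled (sequential MAR) | not filled |
| Week 26 | filled from placebo model | filled (sequential MAR) | filled from retrieved drop-outs |

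The arms differ only in the middle row, and only under wash-out.

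**The plan's own figure.** SAP 1.3 gives about 80% power for a difference of 0.75 with SD 1.7, two-sided alpha 0.05 and 243 subjects (81 per arm). The standard error is 1.7 × √(2/81) = 0.267, and 0.75/0.267 = 2.81. Power is Φ(2.81 − 1.96) = 0.802 (0.797 with the noncentral t), so the figure reproduces. It is not in dispute; its inputs are used below.

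**Expected gap.** Let m be the share of active subjects missing at a visit and δ the effect, with drop-out unrelated to outcome. Wash-out at that visit gives about (1 − m)δ. The data sets as written give about δ. The gap is about mδ, and zero if nobody is missing at that visit.

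**Simulation.** There were 1,500 trials per scenario with 81 per arm, SD of change 1.7 and five imputations. The true effect was 0.4 at Week 6 and 0.75 at Weeks 12, 20 and 26. Drop-out was monotone and non-informative. Assumed missing by Week 26: 2% to 20%, of which 25%, 50% and 80% was already present at Weeks 6, 12 and 20.

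| Missing by Week 26 | m at Week 20 | Active n at Week 20 | Week 20, as written | Week 20, wash-out at every visit | Gap | m × 0.75 | Week 26, both |
|---|---|---|---|---|---|---|---|
| 2% | 1.6% | 79.7 | −0.739 | −0.727 | 0.012 | 0.012 | −0.734 |
| 5% | 4% | 77.8 | −0.739 | −0.710 | 0.029 | 0.030 | −0.704 |
| 10% | 8% | 74.4 | −0.757 | −0.695 | 0.062 | 0.060 | −0.676 |
| 20% | 16% | 68.0 | −0.750 | −0.630 | 0.120 | 0.120 | −0.593 |

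Placebo n is 81 at every visit, and active n returns to 81 at Week 26. The Monte Carlo error of each estimate is about 0.267/√1500 = 0.007, so the small differences down the as-written column are noise.

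**Step from Week 20 to Week 26, with a constant true effect**

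- 10% missing: 0.757 − 0.676 = 0.081 as written, against 0.695 − 0.676 = 0.019 with wash-out at every visit. The change of rule adds 0.062.
- 20% missing: 0.750 − 0.593 = 0.157 as written, against 0.630 − 0.593 = 0.037. The change of rule adds 0.120.

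**The case against.** **The authors may have meant t to be reset at each visit.** SAP 4.1.12 is written for a general Week t. The wash-out section opens by saying that the remaining missing data will be imputed, without limiting this to Week 26. SAP 4.5.2 and 4.5.4 ask for imputation at every scheduled visit up to Week 26. This may well be the intention. But 4.4.4.1 lacks that wording and says instead that the primary data sets are reused. Resetting t produces different imputed values, so the two cannot both hold, and a programmer following the section literally gets the mismatch.

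**Wash-out is only the fallback.** MI-RD is preferred and imputes Week t alone in every regimen, placebo included. This stands, and the point is limited to wash-out. The fallback is a realistic case: SAP 4.1.12 invokes it if any required model has fewer than five retrieved drop-outs, and SAP 4.4.1 presents both methods for the primary endpoint in any event.

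**A reader might infer that the intermediate estimates are biased in favour of the drug.** The check does not support that. With non-informative drop-out they recover the true 0.75; unequal numbers are not bias, and MAR imputation of placebo from placebo data should not by itself move its mean. They are larger only than the deliberately conservative wash-out figure. Nor are these on-treatment completers: subjects who stopped treatment or were rescued but still have data are included.

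**A reader might also infer that the Week 52 analyses share the fault**, since SAP 4.6.2.1 says "Analyses will be based on the same multiply imputed data sets produced for Week 52 assessments". That is not established. The section refers to SAP 4.1.12 for Week 52, but Table 23 lists these analyses as MI under MAR, which fills every visit in every regimen. What does follow is a second Week 26 estimate taken from the Week 52 data sets. It is exploratory, with nominal p-values, and is not an error in itself.

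**Conclusion.** The point holds as a minor inconsistency in a supportive analysis. Under wash-out, 4.4.4.1 as written applies different imputation rules to the two arms at Weeks 6, 12 and 20 and changes the active-arm population at Week 26. The by-visit curve then mixes two estimands.

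The size depends on drop-out, for which the documents give no current rate. On the assumed range, the Week 20 gap relative to wash-out at every visit runs from 0.01 HbA1c points (2% missing by Week 26) through 0.03 (5%) and 0.06 (10%) to 0.12 (20%). The 10% figure is about a quarter of the planned standard error (0.062/0.267 = 0.23). These values rest on an effect of 0.75 at Week 20, non-informative drop-out and 80% of the missingness being present by then.

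The primary Week 26 test and the hierarchy are untouched. Under MI-RD the arms are treated alike, although drop-outs at the intermediate visits remain unimputed in both.

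**What to change.** In SAP 4.4.4.1, replace the sentence on reusing the primary data sets. State that, under wash-out, active-arm values missing at each plotted visit (t = 6, 12, 20 and 26) are imputed from the placebo model for that visit.

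Keep one imputation method for the whole curve. Running MI-RD at t = 6 needs at least five subjects per model who stopped treatment before Week 6 and still have a Week 6 value, which may not be met. If MI-RD has fewer than five retrieved drop-outs at any plotted visit, use wash-out throughout the curve, so that the method does not change along it.

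In SAP 4.6.2.1, reconcile the reference to Section 4.1.12 with the MAR entry in Table 23, and take visits up to Week 26 from the Week 26 analysis so that only one Week 26 estimate is reported.

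The cost is a few more imputation runs and slightly less favourable intermediate estimates.

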4.5 Secondary efficacy endpoint analysis

4.5.1 Hierarchical Testing

Secondary efficacy endpoint analyses will also be performed separately for each drug (dapagliflozin and saxagliptin). For each drug, the following sequential testing order will be employed to control multiplicity of testing for the secondary objectives at a family-wise Type I error rate of 0.05 (2-sided). For each grouping of endpoints, for example for all reduction in HbA1c/FPG from baseline endpoints for the Randomised Subjects Data Set, for each treatment (dapagliflozin and saxagliptin) the same multiple imputation method will be used.

1. Comparison of mean reduction in HbA1c from baseline at Week 26 between the low-dose/high-dose treatment regimen and placebo
2. Comparison of mean reduction in HbA1c from baseline at Week 26 between the low-dose treatment regimen and placebo
3. Comparison of mean reduction in FPG from baseline at Week 26 between overall drug treatment and placebo
4. Comparison of mean reduction in FPG from baseline at Week 26 between the low-dose/high-dose treatment regimen and placebo
5. Comparison of mean reduction in FPG from baseline at Week 26 between the low-dose treatment regimen and placebo
6. Comparison of the percentage of subjects with baseline HbA1c $\geq 7\%$ who achieve an HbA1c level $< 7\%$ at Week 26 between overall drug treatment and placebo
7. Comparison of the percentage of subjects with baseline HbA1c $\geq 7\%$ who achieve an HbA1c level $< 7\%$ at Week 26 between the low-dose/high-dose treatment regimen and placebo
8. Comparison of the percentage of subjects with baseline HbA1c $\geq 7\%$ who achieve an HbA1c level $< 7\%$ at Week 26 between the low-dose treatment regimen and placebo
9. Comparison of mean reduction in HbA1c from baseline at Week 26 between the high-dose and the low-dose in subjects who do not achieve an HbA1c $< 7\%$ at Week 12
10. Comparison of mean reduction in FPG from baseline at Week 26 between the high-dose and the low-dose in subjects who do not achieve an HbA1c $< 7\%$ at Week 12
11. Comparison of the percentage of subjects with baseline HbA1c $\geq 7\%$ who achieve an HbA1c level $< 7\%$ at Week 26 between the high-dose and the low-dose in subjects who do not achieve an HbA1c $< 7\%$ at Week 12

For each drug (dapagliflozin or saxagliptin) if the primary endpoint is significant, the statistical tests will be formally evaluated, starting from the first secondary efficacy endpoint and continuing in the order above. Each secondary endpoint for a given drug will be tested if the previous secondary endpoint is significant at the two-sided 0.05 level. The testing procedure will stop at the first secondary endpoint that does not reach statistical significance. From then onwards, p-values and CIs will continue to be reported, but no claim will be based these p-values. A clear distinction will be made between p-values whereby claims can and cannot be made.

Hierarchical testing of the primary and secondary efficacy endpoints will be presented for either the Randomised Subjects Data Set or Up-titration Randomised Subjects Data Set (as applicable per endpoint). Point estimates, 95% CIs and p-values will be summarised.

4.5.2 Comparison of mean reduction in HbA1c from baseline at Week 26 between the low-dose/high-dose treatment regimen and placebo

Data will be multiply imputed based on the same approach as described for the primary analysis of the primary endpoint in Section 4.4.1 at all scheduled time points up to and including Week 26, and will include all data regardless of rescue medication initiation or adherence. Analysis will be performed by fitting the weighted ANCOVA model described in Section 4.1.9. The analysis model will be evaluated in each imputed data set and the results will be combined using Rubin's rules as described in Section 4.1.12.4.

The weight matrix W1 described in Section 4.1.9 for the comparison of the low-dose/high-dose treatment regimen versus placebo will be used for this analysis.

In addition, a line plot of LS mean \pm 95% confidence interval (CI) by visit up to Week 26 will be displayed.

4.5.2.1 Sensitivity analysis for secondary endpoint of change from baseline in HbA1c at Week 26 between the low-dose/high-dose treatment regimen and placebo excluding data following rescue medication initiation/early treatment discontinuation

The above primary analysis (Section 4.5.2) for the comparison of mean reduction in HbA1c from baseline at Week 26 between the low-dose/high-dose treatment regimen and placebo will be repeated excluding data following rescue medication initiation or early treatment discontinuation but missing data will be imputed assuming MAR as described in Section 4.1.12.5. A weighted ANCOVA model will be used for this analysis.

4.5.2.2 Subgroup analysis for secondary endpoint of change from baseline in HbA1c at Week 26 between the low-dose/high-dose treatment regimen and placebo

The above primary analysis (Section 4.5.2) for the comparison of mean reduction in HbA1c from baseline at Week 26 between the low-dose/high-dose treatment regimen and placebo will be repeated for subgroups based on race, ethnicity, sex, age group (using randomisation strata), region, baseline antidiabetic treatment, baseline HbA1c and baseline BMI, using the categories defined in the Appendix (Table 19) and will follow the same approach as the one described in Section 4.4.3.1 using a weighted ANCOVA model.

4.5.2.3 Metformin subgroup analysis for primary analysis of secondary endpoint of change from baseline in HbA1c at Week 26 between the low-dose/high-dose treatment regimen and placebo

The weighted ANCOVA model used for the primary analysis (Section 4.5.2) of the change from baseline in HbA1c at Week 26 will also be repeated for the subgroup of subjects on a stable baseline dose of metformin IR or XR (with or without insulin). The same multiple imputation method used for the primary analysis of the endpoint will be used for this subgroup analysis. The indicator for background medication used in the multiple imputation step for insulin only and insulin with metformin will be grouped as defined in Section 4.1.12.

4.5.3 Comparison of mean reduction in HbA1c from baseline at Week 26 between the low-dose treatment regimen and placebo

Data will be multiply imputed based on the same approach as described for the primary analysis of the primary endpoint in Section 4.4.1 at all scheduled time points up to and including Week 26, and will include all data regardless of rescue medication initiation or adherence. Analysis will be performed by fitting the weighted ANCOVA model described in Section 4.1.9 in each of the imputed data sets and combining the results using Rubin's rules, as described in Section 4.1.12.4. The weight matrix W2 described in Section 4.1.9 for the comparison of the low-dose treatment regimen versus placebo will be used for this analysis.

4.5.3.1 Sensitivity analysis for secondary endpoint of mean reduction in HbA1c from baseline at Week 26 between the low-dose treatment regimen and placebo excluding data following rescue medication initiation/early treatment discontinuation

The above primary analysis (Section 4.5.3) for the comparison of mean reduction in HbA1c from baseline at Week 26 between the low-dose treatment regimen and placebo will be repeated excluding data following rescue medication initiation or early treatment discontinuation but missing data will be imputed assuming MAR as described in Section 4.1.12.5.

4.5.3.2 Metformin subgroup analysis for secondary endpoint of change from baseline in HbA1c at Week 26 between the low-dose treatment regimen and placebo

The weighted ANCOVA model used for the primary analysis (Section 4.5.3) for the change from baseline in HbA1c at Week 26 will also be repeated for the subgroup of subjects on a stable baseline dose of metformin IR or XR (with or without insulin). The same multiple imputation method used for the primary analysis of the endpoint will be used for this subgroup analysis. The indicator for background medication used in the multiple imputation step for insulin only and insulin with metformin will be grouped as defined in Section 4.1.12.

4.5.4 Comparison of mean reduction in FPG from baseline at Week 26 between overall drug treatment and placebo

Data will be multiply imputed based on the same approach as described for the primary analysis of the primary endpoint in Section 4.4.1 at all scheduled time points up to and including Week 26, replacing HbA1c with FPG, and will include all data regardless of rescue medication initiation or adherence. Only FPG assessments documented with the subject in a fasting state will be summarised and listed. Analysis will be performed by fitting the ANCOVA model described for the primary analysis of the primary endpoint in Section 4.4.1 (replacing HbA1c with FPG). The analysis model will be evaluated in each imputed data set and the results will be combined using Rubin's rules as described in Section 4.1.12.4. No weights will be used in the multiple imputation or ANCOVA for this analysis.

In addition, a line plot of LS mean \pm 95% confidence interval (CI) by visit up to Week 26 will be displayed.

4.5.4.1 Sensitivity analysis for secondary endpoint of mean reduction in FPG from baseline at Week 26 between overall drug treatment and placebo excluding data following rescue medication initiation/early treatment discontinuation

The above primary analysis (Section 4.5.4) for the comparison of mean reduction in FPG from baseline at Week 26 between overall drug treatment (low-dose and high-dose) and placebo will be repeated excluding data following rescue medication initiation or early treatment discontinuation but missing data will be imputed assuming MAR as described in Section 4.1.12.5.

4.5.4.2 Metformin subgroup analysis for comparison of mean reduction in FPG from baseline at Week 26 between overall drug treatment and placebo

The ANCOVA model used for the primary FPG analysis (Section 4.5.4) of the change from baseline in FPG at Week 26 between overall drug treatment and placebo will also be repeated for the subgroup of subjects on a stable baseline dose of metformin IR or XR (with or without insulin). The same multiple imputation method used for the primary analysis of the endpoint will be used for this subgroup analysis. The indicator for background medication used in the multiple imputation step for insulin only and insulin with metformin will be grouped as defined in Section 4.1.12. No weights will be used in the multiple imputation or ANCOVA for this analysis.

